Early Treatment of Cytokine Storm Syndrome in Covid-19

NCT04362111

UAB IRB Final Approval Date: July 28 2020

Protocol

Introduction

Macrophage Activation Syndrome (MAS) or Cytokine Storm Syndrome (CSS) is a disorder consisting of massive systemic inflammation, multi-organ system failure, disseminated intravascular coagulopathy, and often severe morbidity/mortality. Reports from areas initially impacted by Covid-19 confirm clinical and laboratory features present in patients with respiratory failure that are identical to those associated with Cytokine Storm Syndrome (CSS) occurring in the setting of other disorders and viral infections (1,2). The recombinant human IL-1 soluble receptor antagonist (rhIL-1ra) anakinra has a short half-life of 4-6 hours, is quick acting and in multiple case reports/series has been reported to be safe as well as effective in treating CSS occurring in the setting of herpes virus infections (EBV/CMV/HSV), ehrlichiosis, sepsis syndromes, adult Still disease/systemic JIA, and systemic lupus (3-6). In children with severe flares of sJIA, doses as high as 100 mg sc every 6 hours have been employed with success (7) and in the absence of significant noted toxicities. In previous trials of anakinra use for management of sepsis, doses up to 3500 mg/day were employed over 72 hours without any noted serious toxicities attributed to anakinra (8). In a recent study examining outcomes in the phase III sepsis trials, treatment with anakinra was associated with improved survival in a subgroup with MAS attributes including hepatic dysfunction and coagulopathy (4) Trials of anakinra to treat CSS in hospitalized patients with Covid-19 infection and features of CSS are therefore warranted.

Specific Aims

The specific aims of the trial are to determine whether treatment with anakinra added to standard of care treatment for hospitalized patients with Covid-19 pneumonia results in:

1. . Survival and discharge from the hospital without the need for intubation/mechanical ventilation. (Primary outcome)
 1. No increase in oxygen requirement or oxygen delivery measures to maintain $\text{SaO}_2 > 90\%$ at 48 hours compared to baseline at study entry/randomization. (Primary outcome)
 2. No increase in oxygen requirement or oxygen delivery measures to maintain oxygen saturation $>90\%$ Day 2 (48 hours) through Day 105 (120 hours). (Secondary outcome)
 3. At least 25% decrease in serum ferritin, LDH, CRP, and d-dimer at 48 hours. (Secondary outcome)

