 4. Normalization by Day 5 of laboratory CSS attributes: ferritin, fibrinogen, AST, ALT, leucopenia, tryglycerides, sCD25 (Secondary outcome)
 5. Normalization or $\geq 75\%$ improvement by Day 10 (120 hours) in each of the following laboratory CSS attributes elevated beyond the normal range at randomization: ferritin, fibrinogen, AST, ALT, leucopenia, thrombocytopenia, d-dimer, CRP, triglycerides, sCD25. (Secondary outcome)
 6. Decreased time to achievement of $\geq 93\%$ oxygen saturation on room air. (Secondary outcome)
 7. No increased prevalence of nosocomial bacterial or fungal or viral infection through the time of hospital discharge. (Secondary outcome)
 8. No failure to develop neutralizing antibody to Covid-19 measured at Day 28. (Secondary outcome)
5. Discharge from hospital without the need for intubation/mechanical ventilation. (Secondary outcome)

Significance

If shown effective, early identification of CSS and repurposing anakinra for its treatment in severe Covid-19 illness will help reduce ICU admissions, improve patient outcomes and enhance survival.

Confirmation of a genetic basis for susceptibility to Covid-19 associated CSS as we identified in H1N1 associated deaths (6) will also facilitate risk stratification and future targeted approaches to Covid-19 disease management.

Design

Recruitment and Enrollment: Thirty patients will be recruited for enrollment; potential subjects will be identified from the registry of Covid-19 patients admitted to the University of Alabama Hospital.

Patient Compensation: Not applicable

Eligibility/Inclusion Criteria:

Inclusion criteria:

1. 18 years old or older
2. Molecular diagnosis of SARS-CoV-2 infection and Covid-19 pneumonia
3. Radiographic imaging consistent with Covid-19 pneumonia
4. Room air oxygen saturation <93%
5. Hyperferritinemia (>700 ng/ml)
6. Any three of the following:
 - a. elevated d-dimer (> 500 ng/ml)
 - b. thrombocytopenia (< 130,000/mm³)
 - c. leucopenia (WBC < 3500/mm³) or lymphopenia (<1000/mm³)
 - d. elevated AST or ALT (> 2X ULN)
 - e. elevated LDH (> 2X ULN)
 - f. CRP > 100 mg/L

Exclusion criteria:

1. Participation in other investigational treatment protocols for Covid-19 infection
2. Culture confirmed active bacterial infection requiring antibiotic therapy
3. On mechanical ventilation
4. Previous known hypersensitivity reaction to anakinra
5. Previous known hypersensitivity reaction to E Coli derived proteins
6. Pregnant or breast-feeding females

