All adverse events that are deemed to be serious and meet the definitions provided in section 6.1.5.2, for serious adverse events will be reported as SAEs.

SAEs

Any AE that results in any of the following outcomes will be considered an SAE, as per outcomes as defined according to Code of Federal Regulations (CFR) Title 21 part 312.32.

- Death
- Life-threatening situation (subject was at risk of death at the time of the event. This does not refer to an event that might have caused death if it was of greater intensity.)
- Prolongation of existing hospitalization
- Persistent or significant disability or incapacity
- Congenital anomaly or birth defect
- Important medical events that may not result in death, be life-threatening, or require hospitalization but may jeopardize the subject and may require medical or surgical intervention to prevent one of the above outcomes (based upon appropriate medical judgment)

A data safety monitoring board (DSB) comprised of three UAB Rheumatologist, a UAB pulmonary and critical care specialist, a UAB specialist in infectious disease, UAB specialist in hematology, and a UAB specialist in nephrology will meet following enrollment of the first 15 subjects or quarterly to review inter-current study outcomes and safety data. The DSB for this study will also review any and all deaths that occur during the study within two weeks of the time of death. If it is the assessment of the DSB that deaths or other SAEs during the course of the study are significantly more prevalent in the anakinra treatment arm or the placebo arm, the study will be prematurely terminated.

Statistical Analysis Plan

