The primary efficacy analysis will be conducted on a modified intention-to-treat basis and defined as all patients who underwent randomization and received either anakinra or placebo before intubation/mechanical ventilation or death. Descriptive statistics will be used to characterize participants. Continuous data will be summarized by means and standard deviation (SD) and analyzed by student t tests. Categorical data will be described with frequencies and percentages and compared using Fisher's exact or chi square tests. Cox proportional hazards models will be used to calculate hazard ratio for the association between treatment group and death from any cause or need for mechanical ventilation; due to small sample size control for demographic characteristics, clinical variables and comorbidities will likely not be possible. Calculated 95% confidence interval (CI) and $p < 0.05$ will be considered significant. All analysis will be conducted with SAS v 9.4 (Cary, NC, USA).

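### The data safety board must stop the study on a significant placebo excess of deaths or SAEs, which can act as a stop for benefit, yet the SAP keeps p<0.05 with no allowance for the looks

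*Combined protocol and SAP*

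**What the plan says.** The stopping clause is in the SAEs section of the protocol. It begins "If it is the assessment of the DSB that deaths or other SAEs during the course of the study are" and continues "significantly more prevalent in the anakinra treatment arm or the placebo arm, the study will be prematurely terminated". It covers both directions, and termination is mandatory once the board has made that assessment. It names no test, threshold or boundary.

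The same section sets the reviews. The board "will meet following enrollment of the first 15 subjects or quarterly to review inter-current study outcomes and safety data", and it will also "review any and all deaths that occur during the study within two weeks of the time of death". The *or* leaves the schedule open, and the reviews of deaths depend on the data, so the number of looks is not fixed.

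Under Design, "Thirty patients will be recruited for enrollment", randomised 1:1. Specific Aims lists as its first outcome "Survival and discharge from the hospital without the need for intubation/mechanical ventilation. (Primary outcome"). The Statistical Analysis Plan models the "hazard ratio for the association between treatment group and death from any cause or need for mechanical ventilation". For categorical data it allows Fisher's exact test or chi-square, and it takes p<0.05 as significant. It mentions no interim review and does not link its tests or its 0.05 level to the board.

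The other termination criteria, under Withdrawal of Participant Consent and Discontinuation of Study Drug, concern only harm related to study drug. They give no rule for a placebo excess.

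**The concern.** A board that stops because too many placebo patients have died has in effect found benefit on a component of the primary outcome. This has two consequences for how a stopped trial can be read.

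First, if *significantly* means the SAP's p<0.05, the comparison may be tested many times at an unadjusted level, and a chance difference at any look ends the trial. Second, with about seven or eight patients per arm, only a very large observed difference reaches p<0.05. A trial stopped there will on average overstate the effect.

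If the board is meant to use clinical judgement, no error rate can be calculated for a stopped trial. The SAP would still allow a p<0.05 claim from it.

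**Working it through.** **Inputs.** From the documents: 30 patients, 1:1 allocation, a review at 15 patients, a review of each death, level 0.05, Fisher or chi-square. The plan gives no interim boundary or error rate to reproduce.

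**Assumptions.** *Significantly* means two-sided p<0.05. True death rates are equal at 10–50% where error is calculated. Outcomes are known immediately. The split is 15 v 15 at the end and 7 v 8 or 8 v 7 at 15 patients. Chi-square is uncorrected.

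**1. What a stop at 15 requires (7 placebo, 8 anakinra).**
- Fisher, 4/7 v 0/8 deaths: p = C(7,4)/C(15,4) = 35/1365 = 0.026. The opposite extreme, 0/7 v 4/8, has probability 70/1365 = 0.051. That is larger, so it is not added. Observed excess: 4/7 = 57 points.
- Chi-square, 3/7 v 0/8 deaths: 15 × (3×8 − 4×0)² / (7×8×3×12) = 8640/2016 = 4.29, p = 0.038. Observed excess: 3/7 = 43 points.
- Fisher on 3/7 v 0/8: 35/455 = 0.077.

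On the same data, one permitted test therefore stops the study and the other does not. Over all tables at 7 v 8 and 8 v 7, the smallest qualifying placebo excess is 57 points (Fisher) or 43 points (chi-square).

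**2. Looks at 15 and 30 only, no true difference (exact enumeration).** The chance of p<0.05 at either look is 3.3–8.5% by chi-square and 0.6–4.5% by Fisher. The normal approximation for two equally spaced looks gives 8.3%.

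**3. Looks after each death and at 15 and 30, no true difference.** Simulated with 20,000 trials per row; the final-look-only columns are exact. Entries are the percentage of trials with a significant death difference.

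| Death rate | Mean looks | Fisher: any look | of which placebo worse | Fisher: final only | Chi-square: any look | of which placebo worse | Chi-square: final only |
|---|---|---|---|---|---|---|---|
| 10% | 4.8 | 1.5 | 0.7 | 0.6 | 7.3 | 3.7 | 2.5 |
| 20% | 7.6 | 5.0 | 2.4 | 1.7 | 15.3 | 7.7 | 5.0 |
| 30% | 10.4 | 7.8 | 3.8 | 1.7 | 19.7 | 9.8 | 5.5 |
| 40% | 13.2 | 8.8 | 4.4 | 1.6 | 21.4 | 10.5 | 4.9 |
| 50% | 16.0 | 9.5 | 4.8 | 1.7 | 22.8 | 11.5 | 4.6 |

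Quarterly meetings and tests on other SAEs are left out. They would add looks.

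**4. Exaggeration after a stop at 15.** Weight each qualifying table by its binomial probability; the mean observed difference given a stop is Σ(weight × difference)/Σ(weight). With assumed true death rates of 40% placebo v 20% anakinra, 6–9% of trials stop by Fisher and show a mean difference of 63–65 points. By chi-square, 11–14% stop and show 55–58 points. The true difference is 20 points, so the overstatement is about threefold. With 60% v 10%, 42–49% stop by Fisher and show 68–70 points against a true 50.

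**5. Check of the remedy.** At 7 v 8, Fisher p<0.001 requires 7/7 v 0/8: p = 1/C(15,7) = 1/6435 = 0.00016. By normal approximation, one look at p<0.001 followed by 0.05 at the end gives 5.02% overall, so the final level need not be lowered.

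**The case against.** The strongest reply is that the clause calls for an assessment by a board described only by clinical specialties, sits in a safety section, and is never linked to the SAP's p<0.05. Discretionary safety judgement is a natural reading. That stands: the error figures are conditional on one reading, and the text does not settle which was meant. It does not remove the point, because under judgement the SAP would still accept p<0.05 from a trial stopped on the outcome being tested.

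It is also fair to say that:
- The SAP's methods are not limited to a completed trial. What is missing is an allowance or caveat for an early stop.
- The 15-patient review follows enrolment, so some outcomes may be incomplete. Immediate outcomes are an idealisation.
- The figures concern deaths. The SAP's Cox model uses death or ventilation, so they are not the error rate of that model.
- The death rates are assumed, and 60% v 10% has no support in the documents.
- The move of deteriorating control patients to anakinra, described under Design, could narrow the difference between arms and is not modelled.

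A reader might infer more than this. One inference is that the trial has a type I error of 7–23%; the documents state no such rule, and with Fisher at 15 and 30 only the figure stays below 5%. Another is that exaggeration is the main harm and error inflation is minor; that holds only for a single interim look, and the protocol also provides for review of every death. A third is that the placebo direction should be removed from the clause, or the final level cut to 0.048. Removal would also drop the rule for a placebo excess of other SAEs and restrict the board, and neither change is needed to prevent an unsupported claim.

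**Conclusion.** The point holds and should be acted on. The placebo-excess direction can act as a stop for benefit, the number of looks is open, and the SAP makes no allowance for either. If *significantly* means p<0.05, repeated looks raise the chance of a false significant death difference several-fold above that of a single final look: to about 7–23% by chi-square or 1.5–9.5% by Fisher. Both the false-positive risk and the exaggeration after a stop matter, and neither is ranked above the other here. The numbers are illustrative and depend on the assumptions listed. If judgement was meant, the error rate of a stopped trial is unknown and the documents should say so. The gap in the text is certain; its numerical size is not.

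**What to change.** In the SAEs section, leave the board's power to stop in either direction as written, and state that its assessment is a judgement on safety.

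Add to the Statistical Analysis Plan:

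> If the study stops early on a placebo excess of deaths or SAEs, results are reported as estimates with confidence intervals, the report states that the effect is likely overestimated, and no significance claim is made at p<0.05. A claim of benefit from an early stop requires two-sided Fisher exact p<0.001 on all-cause deaths by randomised arm (Haybittle-Peto). The final level stays at 0.05 if the study runs to 30 patients.

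Counting by randomised arm has to be written down because control patients who deteriorate can move to anakinra, and their deaths could otherwise be credited to either treatment.

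**Cost.** Wording only; no extra patients or data. A trial stopped early on a less extreme difference can no longer claim significance. Under assumed death rates of 60% v 10%, the chance of a claimable result at 15 patients falls from 42–49% (Fisher p<0.05) to about 1%. The threshold does not cure exaggeration in a trial that does stop, which is why the report must state it. The board's ability to protect patients is unchanged.

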Subjects in the SoC only arm with deterioration of respiratory parameters and CSS markers at 48-96 hours will be transitioned to treatment with anakinra. Patients will stay on anakinra until all CSS markers no longer exceed the thresholds required for enrollment or through Day 5 of anakinra treatment, whichever comes first. Anakinra may be continued after Day 5 of treatment at the discretion of the treating physicians.

Informed Consent:

Identified patients who may be eligible for enrollment will be asked to consider participation in the protocol in the context of the informed consent process whereby the risks and benefits of their participation are discussed with a study investigator. As subjects with CSS/MAS are often severely ill,

those with any suspected altered sensorium will not be enrolled without the assent of a family member who is the designated representative of the patient to assist with their decision whether or not to participate.

Randomization:

Randomization will be assigned by the study coordinator using a computer-based randomization algorithm. The respective PIs will remain blinded to treatment group assignment for all subjects until study completion.

Visit Schedule and Study Procedures

Following obtaining informed consent and 1:1 randomization by computer, study assessments will be as follows:

Day 0:

- Record vital signs, ventilation and oxygen support, heart function, and kidney function/support.
- Blood drawn for these tests:
 - ferritin, CBC with diff, CMP, ESR, CRP, fibrinogen, D-dimer, INR/PT, LDH triglyceride level
 - Cytokine-12 panel, IL-18, CXCL9, sCD25, sCD163, IL-1 β , NK/B/T-cell lymphocytes
 - NK cell function assay
- Blood sample for genetic testing for perforin pathway (genetic traits associated with CSS)

Every effort will be made to procure remdesivir as available under existing PUA for all enrolled subjects.

Following completion of the baseline assessments, dosing of study agent (100 mg anakinra or equal volume saline placebo) will commence every 6 hours by subcutaneous administration.

Day 1-Day 9:

- Record vital signs, ventilation and oxygen support, heart function, and kidney function/support.
- Blood drawn for these tests: ferritin, CBC with diff, CMP, ESR, CRP, fibrinogen, D-dimer, INR/PT, LDH

Day 10:

- Record vital signs, ventilation and oxygen support, heart function, and kidney function/support.
- Blood drawn for these tests:

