 - ferritin, CBC with diff, CMP, ESR, CRP, fibrinogen, D-dimer, INR/PT, LDH, triglyceride level
 - Cytokine-12 panel, IL-18, CXCL9, sCD25, sCD163, and subsets of NK/B/T-cell lymphocytes

If after Day 5 but before Day 10, lab studies show that the levels of ferritin, d-dimer, CRP, LDH, AST, ALT have all returned to normal or improved $\geq 75\%$ from noted Day 0 elevations in these laboratory tests AND the subject has $\geq 93\%$ saturation on room air oxygen, the dose of IP will be decreased to twice daily until Day 10.

All study participants will continue to receive current standard of care treatment for Covid-19 infection. It is understood the standard is evolving and that some treatments that are newly considered standard of care (such as remdesivir) may not be available to enrolled subjects.

Withdrawal of Participant Consent and Discontinuation of Study Drug:

Study participation may be discontinued for any of the following reasons:

- a. Subject decision to withdraw consent for study
- b. Evidence of allergy to administered anakinra
- c. Intolerable adverse event as judged by study investigator and participant
- d. Decision to terminate the study by the investigator and the DSMB due to one or more of the following:
 - Death in any subject in which the cause of death is judged to be probably or definitely related to the study drug by the treating investigator.
 - The occurrence in any subject of a life-threatening SAE whose causal relationship to study drug is judged to be probable or definite by the treating investigator.
 - Two occurrences of Grade 3 or higher toxicities (per NCI CTCAE) that are assessed to be related to the study drug by the investigator.
 - Two occurrences of a clinically significant Grade 3 or higher laboratory abnormality (per NCI CTCAE) assessed to be related to the study drug by the investigator.

If the study drug is discontinued, unless the subject withdraws consent, the subject will be followed for the full treatment/observation period (through Day 60) and all data will be collected as scheduled.

If the study drug is discontinued, unless the subject withdraws consent, the subject will be followed for the full treatment/observation period and all data will be collected as scheduled.

Data Collection:

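### Secondary and exploratory continuous data go to an unadjusted Student t test with no transformation or rank method, which wastes power if the values are right-skewed

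*Combined protocol and SAP*

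**What the plan says.** The Statistical Analysis Plan is a single paragraph. For continuous variables it states: "Continuous data will be summarized by means and standard deviation (SD) and analyzed by student t tests". For yes/no variables: "Categorical data will be described with frequencies and percentages and compared using Fisher's exact or chi square tests". Death or mechanical ventilation goes to a Cox model. The significance rule is "Calculated 95% confidence interval (CI) and $p < 0.05$ will be considered significant". The paragraph acknowledges the small sample only when discussing covariates in the Cox model. Neither it nor the rest of the protocol mentions a log transformation, median and IQR, a rank test, a distribution check or the Day 0 value as a covariate for continuous data.

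On size, the Design section says "Thirty patients will be recruited for enrollment", and the visit schedule specifies 1:1 randomization.

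The Day 10 visit draws "Cytokine-12 panel, IL-18, CXCL9, sCD25, sCD163, and subsets of NK/B/T-cell lymphocytes". The same cytokines and soluble receptors are drawn on Day 0. Ferritin, CRP, d-dimer and LDH, with CBC and CMP, are measured daily. Data Collection adds ICU and hospital duration.

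The laboratory items in the Specific Aims are responder definitions: at least a 25% decrease at 48 hours, normalization by Day 5, and normalization or at least 75% improvement by Day 10.

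**The concern.** Cytokines, ferritin, d-dimer, CRP, LDH, transaminases and lengths of stay are positive values with no natural ceiling, and a few patients may have values several times the median. On the raw scale such values inflate the SD and dominate the mean, so with at most 15 patients per arm a t test can miss a real reduction. The protocol itself judges marker change in percent, which is a ratio scale, whereas a raw t test compares additive means. An unadjusted test also sets aside Day 0 values that the trial already collects. At stake is the mechanistic reading of the trial: whether anakinra lowered markers for which no responder rule is given.

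**Working it through.** **No figure to reproduce.** The documents give no SD, effect size or power for any continuous variable. The check therefore compares tests over a range of assumptions.

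**Inputs from the documents.** N = 30 at 1:1, so 30/2 = 15 per arm at most; alpha 0.05, taken as two-sided to match the 95% CI (the SAP does not state sidedness).

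**Assumptions.** Log-normal values; log-SD from 0.5 to 1.5; a true ratio of geometric means of 0.5 or 0.35; Day 0/Day 10 log-correlation 0.5; all 30 patients have a Day 10 value; no control patient switches to anakinra.

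**Formulas.** On the log scale, SE = SD × √(2/15), and the noncentrality is |ln(ratio)|/SE. ANCOVA replaces SD by SD × √(1 − 0.5²) = 0.866 × SD. For log-SD 1.0 and ratio 0.5:
- log t: SE = 1.0 × 0.365 = 0.365; noncentrality 0.693/0.365 = 1.90; power 45% on 28 df
- log ANCOVA: SE = 0.866 × 0.365 = 0.316; noncentrality 0.693/0.316 = 2.19; power about 55% on 27 df

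The raw t test has no simple formula here and was simulated.

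**Power with 15 per arm**

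| Log-SD | Ratio | Raw t | Log t | Log ANCOVA |
|---|---|---|---|---|
| 0.5 | 0.5 | 93% | 96% | 99% |
| 0.8 | 0.5 | 51% | 64% | 75% |
| 1.0 | 0.5 | 30% | 45% | 55% |
| 1.5 | 0.35 | 20% | 46% | 55% |

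The step from raw t to log t (3, 13, 15 and 26 points) is the cost of skew. The step from log t to ANCOVA (3, 11, 10 and 9 points) is the value of the Day 0 measurement. They are separate gains.

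**Type I error of the raw t test.** About 4% at log-SD 0.8, 3.5% at 1.0 and 2.4% at 1.5. The log t test stays near 5%.

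**Extreme patients.** This is a constructed example: 15 per arm at fixed log-normal quantiles, log-SD 0.8, true ratio 0.4, with the top one or two patients in each arm set to 10 times the control median.

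| Case | Raw t | Log t | Rank-sum |
|---|---|---|---|
| No extremes | p = 0.014 | p = 0.004 | p = 0.005 |
| One per arm | p = 0.49 | p = 0.028 | p = 0.0075 |
| Two per arm | p = 0.67 | p = 0.084 | p = 0.014 |

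With two extremes per arm the log t test also passes 0.05 and only the rank test holds, so logging alone does not fully protect against outliers.

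**The case against.** The strongest case against is one of relevance. No stated aim compares a continuous marker between arms. The laboratory aims are yes/no and go to Fisher's exact or chi-square; death or ventilation goes to Cox. IL-18, CXCL9 and sCD163 are drawn but appear in no aim, and the t-test sentence is a general one that follows a remark on describing participants. This stands, and it limits the point to secondary or exploratory comparisons. A reader might infer that a t test of these three cytokines is a specifically planned analysis. The documents do not say so; it is only the method that the general rule would give them.

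Second, the skew is assumed. A reader might take the entry criteria as proof of long right tails. Only ferritin (above 700 ng/ml) has a mandatory floor. D-dimer, LDH and CRP are options under an any-three-of list, the three cytokines have no entry criterion, and a Day 0 cutoff does not fix the shape of a Day 10 distribution. This stands too, which is why the range includes log-SD 0.5, where the loss from skew is about 3 points.

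Third, the simulated trial is cleaner than the real one. Control patients who deteriorate move to anakinra at 48-96 hours, before Day 10, and death or discharge can remove Day 10 values. If 20% or 40% of controls switch with full effect (assumed shares), log ANCOVA at log-SD 1.0 and ratio 0.5 falls from about 55% to 36% or 23%. This lowers the absolute powers for every method, but it does not make the raw t test a better choice.

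Finally, that the test is on the raw scale is inferred from silence. It is nonetheless the plain reading of a rule that names no transformation.

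**Conclusion.** The point holds as a minor one. The SAP's rule for continuous data is less efficient than an available alternative that uses data already collected. For a true halving with 15 per arm, moving from raw t to log ANCOVA gains about 6 points of power at log-SD 0.5 (93 to 99%), 24 at 0.8 (51 to 75%) and 25 at 1.0 (30 to 55%). At log-SD 1.5 with ratio 0.35 the gain is 35 points (20 to 55%). These figures rest on log-normality, the assumed log-SDs, the 0.5 correlation and complete Day 10 data without switching.

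Two stronger conclusions are not supported. A reader might infer that the main efficacy result is at risk; it is not, since the primary outcomes and the responder-type laboratory aims use other methods. A reader might also infer that the trial could report spurious marker effects from this cause; under the assumed skew the raw t test rejects too rarely, about 3-4% at log-SD 0.8 to 1.0 and less at 1.5. The risk is that a real effect on a marker is reported as null.

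**What to change.** In the Statistical Analysis Plan, replace the single rule for continuous data with the following:

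- **Named list to be log-transformed:** cytokines and soluble receptors, ferritin, d-dimer, CRP, LDH, AST, ALT and triglycerides. Summarise by median (IQR) and geometric mean. Compare arms by ANCOVA on the log value with the log Day 0 value as covariate, and report the ratio of geometric means with its 95% CI.
- **Sensitivity analysis:** a Wilcoxon rank-sum test for every variable on that list, always run and not triggered by how the data look. This covers extreme values, against which the log-scale analysis is not fully robust.
- **ICU and hospital duration:** median (IQR) and Wilcoxon rank-sum test.
- **Remaining continuous variables:** a named list for which mean, SD and t test are kept, so that no choice is left until after the values are seen.

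The cost is SAP wording only. No extra patients, visits or samples are needed, because the Day 0 values are already scheduled. The small downside is that results are reported as ratios rather than mean differences.

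### Two outcomes are labelled primary at p<0.05 with no success rule and an open choice of test, so the false-claim rate can exceed 5% and the choice of test can change the verdict

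*Combined protocol and SAP*

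**What the plan says.** The Specific Aims give the primary label to two yes/no outcomes. The first is "Survival and discharge from the hospital without the need for intubation/mechanical ventilation. (Primary outcome"). The second is no increase in oxygen need "at 48 hours compared to baseline at study entry/randomization. (Primary outcome"). The last item of the same list labels discharge without ventilation as secondary, which nearly repeats the first primary outcome. The numbering of the list is irregular: the second primary outcome is nested under the first, and an item 5 follows item 8.

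The Statistical Analysis Plan gives the test, "Categorical data will be described with frequencies and percentages and compared using Fisher's exact or chi square tests", and the threshold, "Calculated 95% confidence interval (CI) and $p < 0.05$ will be considered significant". It does not say when each test applies or whether the chi-square is continuity-corrected. It also says "Cox proportional hazards models will be used to calculate hazard ratio for the association between treatment group and death from any cause" or need for ventilation, without giving that model a role.

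On size, the Design section says "Thirty patients will be recruited for enrollment". Allocation is 1:1, but no blocking is described: "Randomization will be assigned by the study coordinator using a computer-based randomization algorithm". The efficacy set is limited to randomized patients who "received either anakinra or placebo before intubation/mechanical ventilation or death", so the analysed arms need not be equal.

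**The concern.** Two outcomes, one threshold and no success rule leave open what counts as a positive trial. The text does not exclude a claim based on whichever outcome reaches 0.05, and that gives chance two opportunities. With about 15 patients per arm the choice between Fisher and chi-square also matters, because the two can fall on opposite sides of 0.05 for the same counts. If the outcomes or the tests diverge, a reader could not tell from the plan whether the trial succeeded.

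**Working it through.** **Inputs from the documents.** 30 patients, 1:1 allocation, two primary labels, threshold 0.05, Fisher or chi-square. The plan gives no event rate, effect size or power, so it has no figure of its own to reproduce.

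**Assumptions.** Two-sided tests; common success rate under no effect taken over its whole range; independent outcomes unless stated; errors in both directions counted; seven splits near 15 v 15, since equal arms are not assured. The expected-count convention means Fisher if any expected count is below 5, otherwise uncorrected chi-square.

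**Step 1: nominal rate.** If either outcome suffices, 1 - (1 - 0.05)² = 9.75%.

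**Step 2: actual rate.** Every 2x2 table was enumerated with exact binomial probabilities. The single-test size was maximised over the null rate, and the either-outcome error is 1 - (1 - size)². For uncorrected chi-square at 15 v 15 the size is 5.50%, so 1 - (1 - 0.0550)² = 10.7%.

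| Split | Uncorrected chi-square | Convention | Fisher |
|---|---|---|---|
| 15 v 15 | 10.7% | 8.4% | 3.5% |
| 14 v 16 | 11.5% | 8.4% | 6.2% |
| 15 v 14 | 12.0% | 11.2% | 5.5% |
| 15 v 13 | 12.5% | 9.2% | 5.8% |
| 13 v 17 | 10.5% | 8.1% | 5.7% |
| 14 v 14 | 10.1% | 7.0% | 4.2% |
| 14 v 13 | 10.3% | 10.2% | 6.4% |

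With Yates' correction the figure is 3.3% at 15 v 15 and at most 4.8% at any of the seven splits.

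**Step 3: how far this depends on the assumptions.**
- Success rate, 15 v 15: at 80% the convention gives 3.7%; at 90% the figures are 4.9% (uncorrected chi-square), 1.1% (convention) and 1.1% (Fisher).
- Correlation 0.5, rates 50-70%, 15 v 15: 8.4-10.0%, 5.4-7.7% and 3.1-3.2% in the same order.
- False claims favouring one given arm: about half. For uncorrected chi-square at 15 v 15, 1 - (1 - 0.0550/2)² = 5.4%.
- Both outcomes required: at most 1.9% (uncorrected chi-square) or 0.5% (Fisher) in the settings run.

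**Step 4: choice of test.** Take 6/15 v 12/15. Uncorrected chi-square = 30 × (6×3 - 9×12)² / (15×15×18×12) = 30 × 8,100 / 48,600 = 5.0, p=0.025. Fisher gives p=0.060 and Yates p=0.062. The expected counts are 9 and 6, so the convention would select chi-square. Of the 256 possible tables at 15 v 15, 24 are significant by uncorrected chi-square only and none by Fisher only; with Yates only 4 disagree with Fisher. At an assumed 50% v 80%, uncorrected chi-square and Fisher disagree in 17% of 15 v 15 trials.

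**Step 5: what controls the error.**
- Splitting alpha alone is not enough. At 0.025 each, uncorrected chi-square still reaches 7.1% (15 v 13) and the convention 6.9% (14 v 14).
- Naming a test alone is not enough either. Boschloo at 0.05 has size up to 4.86% (13 v 17), so two outcomes give 1 - (1 - 0.0486)² = 9.5%.
- Together they work. At 0.025 the largest size is 2.49% for Boschloo and 1.92% for Fisher. Under any dependence, two outcomes give at most 2 × 2.49% = 4.98% and 2 × 1.92% = 3.84%. Holm's second step, at 0.05, has size at most 4.86% (Boschloo) or 3.26% (Fisher).

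**The case against.** The strongest reply is that inflation is not built into the plan. The documents give no event rate, so nothing favours the worst case. Yates' correction keeps the either-outcome error below 5% at every split examined, and so does Fisher at 15 v 15 and 14 v 14. If both outcomes must succeed the issue disappears. The conflicting labels may even mean that only one primary outcome is intended, in which case no multiplicity arises. All of this stands, and it limits the claim to an error that can exceed 5%. It does not remove the point, because the plan selects none of these safe options, and Fisher exceeds 5% at all five unequal splits.

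A second reply is that preferring Boschloo is a matter of taste. That is fair: Fisher under the same rule also holds the error, and Boschloo only adds power.

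Two stronger readings are tempting. One is that the trial has a false-positive rate of about 10%. The documents do not support it, because that figure needs an either-outcome rule, uncorrected chi-square and unfavourable null rates together. The other is that the Cox model offers a further route to claiming the first primary outcome. Its event is death or ventilation, which omits discharge, so it is a different endpoint; the SAP uses it to obtain a hazard ratio and assigns categorical data to the other tests. Its role does need stating, but nothing shows that it decides a primary outcome.

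**Conclusion.** The concern holds in conditional form and should be fixed. As written, the plan permits a claim on either primary outcome at 0.05, with worst-case error of 10-12.5% (uncorrected chi-square), 7-11% (convention) or 3.5-6.4% (Fisher). These figures rest on independent outcomes, two-sided tests, errors in both directions and the least favourable null rate. The dependence of the verdict on the test is firmer, because a single table shows it, although it mainly concerns the uncorrected chi-square. Confidence is high on the text and on the enumeration. The event rates are assumptions throughout.

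**What to change.** Before unblinding:

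1. Reconcile the primary and secondary labels in the Specific Aims, and carry the result into the SAP. If one primary outcome remains, test it at two-sided 0.05. If both remain, use Holm: each is tested at two-sided 0.025 and, if one is significant, the other is tested at two-sided 0.05.
2. For the binary primary outcomes, replace the open choice with one named test. Use Fisher's exact test, or Boschloo's test with tables ordered by the two-sided Fisher p-value if the software named in the SAP can run it. Report the risk difference with its 95% CI.
3. State that the Cox model for death or ventilation is supportive.

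The cost is wording; no patients or data are added. With two primaries at an assumed 50% v 80% and 15 v 15, moving from 0.05 to 0.025 lowers power per outcome from about 37% to 29% with Boschloo, or from 25% to 18.5% with Fisher, before Holm's second step recovers some of it. With one primary outcome there is no such loss.
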